### **14.6 Safety Analysis**

#### **14.6.1 Extent of Exposure**

All patients who qualify for the study are expected to receive ENVARSUS XR for 3 months. Duration and total doses of ENVARSUS XR will be summarized for period up to Visit 3 and Visit 4. Reasons for dose change will be listed.

All analyses will be based on Safety analysis dataset.

#### **14.6.2 Adverse Events**

The Medical Dictionary for Regulatory Activities (MedDRA) will be used to classify all Aes with respect to system organ class and preferred term. Adverse events will be summarized by presenting the number and percentage of patients having any AE, having an AE in each body system, and having each individual AE preferred term. Any other information collected (e.g., severity or relatedness to study drug) will be listed as appropriate. Incidence of Aes/SAEs will be summarized up to Visit 4. All analyses will be based on Safety analysis dataset.

#### **14.6.3 Other Analysis**

Trough level of ENVARSUS XR at individual scheduled visits will be summarized. Changes from baseline value will be described as well. Vital signs will be summarized similarly. The analyses will be based on Safety analysis dataset.

## **14.7 Interim Analysis**

An interim analysis will be conducted when cognitive data are available for 17 evaluable patients who have completed Visit 3. An estimate of the variation and effect of ENVARSUS XR for CPT-III omission measures will be calculated. A sample size adjustment may be made according to the algorithm described in [Section 14.1](#). Given the exploratory nature of the study, the final analyses described above will not be adjusted for this additional look. The inflation of type I error is minimum ( $\sim 0.005$ ).

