#### **Evaluation Criteria:**

The primary endpoint is:

- Change in cognitive function from Visit 2 to Visit 3, as measured by the Global Composite Score on the Repeatable Battery for the Assessment of Neuropsychological Status (RBANS) , or the global composite score of the Covid-19 Telephone Battery, should that be the primary outcome battery that we employ. The secondary endpoints are as follows:

- Change in cognitive function from Visit 2 to Visit 3, as measured by the following:
- Trail Making Test A & B ([TMT-A, TMT-B] visual attention/executive functioning)
- Change in QoL from Visit 2 to Visit 3 and from Visit 2 to Visit 4, as measured by WHODAS.
- Assessment of Patient Global Impression of Improvement and Clinical Global Impression of Improvement (PGI-I and CGI-I, respectively) at Visit 3.
- Change in quality of sleep from Visit 2 to Visit 3, as measured by the Pittsburgh Insomnia Rating Scale-20 Item Version (PIRS-20)
- Safety evaluation will include adverse events (AEs), serious AEs (SAEs), vital sign measurements, and physical examinations.

Should safety precautions for COVID-19 preclude us from seeing patients in person, neurocognitive function will be assessed via a phone battery derived from standard cognitive tests and proven feasible and valid to assess memory, attention, reasoning, and executive function. These will include the TICS (Telephone interview for Cognitive Testing), WAIS-IV (Digit Span and Similarities), WMS-IV (Logical Memory I & II), Controlled Oral Word Association (COWA), and Hayling Sentence Completion. Psychological status will be assessed using the Beck Depression Inventory II (BDI-II) and the Posttraumatic Stress Disorder-8 (PTSD-8). Quality of life will be assessed using the WHODAS. Age, race, sex, and level of education will also be collected.

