## **6.2 Study Endpoints**

### **6.2.1 Primary Efficacy Endpoint**

The primary efficacy endpoint is the change in cognitive function from Visit 2 to 3 as measured by the Global Cognition Score on the RBANS, a composite score reflecting performance in areas of immediate and delayed memory, visuospatial construction, language, and attention.

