## 14.1 Sample Size

The study aims to enroll approximately 60 patients. With an expected drop-out rate of 10% to 15%, a maximum of fifty-two (52) evaluable patients are expected to reach the end of study.

In order to detect an effect size of 0.5 with 80% power and a one-sided type I error rate of 0.025, a sample size of 34 evaluable patients is needed. (NOTE: We simply need at least 34 patients to have adequate power, but we anticipate approximately having 52, meaning that this study will almost certainly NOT be underpowered). An interim analysis will be conducted when data are available for 17 (half of 34) evaluable patients, to better estimate the variation and effect of the treatment.

The rule for sample size adjustment is as follows:

Denote the planned sample size  $(n) = n_1 + n_2$ , where  $n_1 = 17$ ; and  $n = 34$  (i.e.,  $n_2 = 17$ ) Let

$r=1.5$  be the rate of adjustment (which leads to the maximum sample size of 52). Define

$N_{\text{new}}$  (final sample size) as

$$N_{\text{new}} = \begin{cases} n_1 + K, & n \leq N \leq rn \\ n, & N < n \\ rn, & N > rn \end{cases}$$

where  $K$  is the calculated additional required sample size (beyond first 17 evaluable patients) and  $N$  is the calculated total required sample size based on the observed change and variation from the interim analysis.

The range of possible total sample sizes based on the interim analysis is from 34 and 52, i.e., the sample size remains at 34 if the adjusted estimate is below 34, and increases to a maximum of 52 if the adjusted estimate is beyond 52.

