### **14.5 Efficacy Analysis**

#### **14.5.1 Primary Efficacy Analysis**

The primary efficacy endpoint is the Global Composite Score on the RBANS. Raw scores on the RBANS will be age adjusted and converted into a series of Index Scores (reflecting domains such as immediate memory, delayed memory, attention, etc.) which will in turn be combined to generate the aforementioned Global Composite Score, a summary score reflective of overall neuropsychological status (scores have a mean of 100, SD of 15, impairment is typically defined as a score of <78). Descriptive summaries of patients' scores and percentiles at baseline (i.e., Visit 2) and post-baseline (i.e., Visit 3) will be provided. The mean change (absolute change) in -score

the RBANS composite score from baseline to post-baseline will be evaluated at 0.05 significance level and analyses will be conducted based on both ITT and Evaluable analysis datasets.

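### The interim sample-size re-estimation uses CPT-III omission scores, a test that the protocol neither schedules nor lists as an endpoint

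*Combined protocol and SAP*

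**What the plan says.** The trigger for the interim is set in Section 14.7: "An interim analysis will be conducted when cognitive data are available for 17 evaluable patients who have completed Visit 3". The next sentence names the outcome to be estimated: "An estimate of the variation and effect of ENVARSUS XR for CPT-III omission measures will be calculated". Then: "A sample size adjustment may be made according to the algorithm described in" Section 14.1. The synopsis (Interim Analysis) names the same outcome.

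Section 14.1 names no outcome. It says only that N "is the calculated total required sample size based on the observed change and variation from the interim analysis". CPT-III omission is therefore the only input specified for the rule.

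The outcome actually tested is different. Section 14.5.1 states: "The primary efficacy endpoint is the Global Composite Score on the RBANS". Section 6.2.1 agrees: "The primary efficacy endpoint is the change in cognitive function from Visit 2 to 3 as measured by the Global Cognition Score on the RBANS". The synopsis (Evaluation Criteria) adds an alternative: "or the global composite score of the Covid-19 Telephone Battery, should that be the primary outcome battery that we employ".

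**The concern.** A re-estimation rule driven by the observed effect must use the outcome on which the trial is judged, and the data must be collected. Neither condition is met here.

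If no CPT-III data exist when 17 evaluable patients have completed Visit 3, then N and K cannot be calculated. Someone would have to choose a substitute (RBANS, TMT-A, TMT-B or the telephone composite) in an open-label study after results are available. If CPT-III were obtained outside the schedule, its mean change and SD would decide whether the trial ends at 34 or continues to the cap, whatever RBANS shows.

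**Working it through.** **1. Where CPT-III appears.**

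| Place | Cognitive outcomes named | CPT-III? |
|---|---|---|
| Interim analysis (synopsis; 14.7) | CPT-III omission | yes |
| Endpoints (synopsis; 6.2.1, 6.2.2) | RBANS, TMT-A, TMT-B; telephone composite as alternative primary in the synopsis | no |
| Schedule of activities | TMT-A/B, RBANS, telephone battery | no |
| Test sequence (6.1; 10.1.2 to 10.1.4) | RBANS, TMT-A/B | no |
| Assessment descriptions, body of 10.2.2 | RBANS, TMT-A/B | no |
| Evaluable Dataset (synopsis) | RBANS, TMT-A/TMT-B | no |
| Table of contents, entry 10.2.2.6 | TMT and CPT-III | yes |

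The body of 10.2.2.6 covers only the Trail Making Tests. Apart from the contents entry, the remaining traces are the abbreviation HRT and some references. No current text says that CPT-III will be administered.

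**2. The plan's own figure.** Inputs from 14.1: effect size d = 0.5, 80% power, one-sided alpha 0.025. The test is the paired t-test (synopsis, Analysis Methods). The normal approximation is ((1.960 + 0.842)/0.5)² = 31.4, so 32. The exact noncentral-t calculation gives power 0.795 at n = 33 and 0.808 at n = 34. The stated 34 is reproduced and is not in question.

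**3. What the rule does.** Section 14.1 gives no formula for N. I assume the same paired-t calculation at 80% power and one-sided 0.025, with the observed standardised change d1 (mean change divided by its SD) in place of 0.5:

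- d1 of about 0.495 or more: N is at most 34, so the size stays at 34.
- d1 = 0.45: N = 41. d1 = 0.41: N = 49.
- d1 of about 0.40 or less: the cap.

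The formula cap is r × n = 1.5 × 34 = 51. The stated maximum is 52, which would need r = 52/34 = 1.53.

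**4. Size of the effect if CPT-III were used.** The documents give no effect for either test, so the values below are assumptions. I simulated the rule with 17 interim patients, limits 34 and 51, independent tests and 200,000 runs per case. Each cell gives power of the final RBANS test, with mean N in brackets.

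| True RBANS d | Rule on RBANS | On CPT-III, d = 0 | On CPT-III, d = 0.5 | On CPT-III, d = 0.8 |
|---|---|---|---|---|
| 0.3 | 0.54 (45.9) | 0.55 (50.3) | 0.46 (40.9) | 0.41 (35.4) |
| 0.4 | 0.77 (43.5) | 0.79 (50.3) | 0.69 (40.9) | 0.63 (35.4) |
| 0.5 | 0.92 (40.9) | 0.93 (50.3) | 0.86 (40.9) | 0.82 (35.4) |

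With CPT-III d = 0.5, the size stays at 34 in about 52% of runs and reaches the cap in about 34%. With CPT-III d = 0, about 94% reach the cap, so the cost is patients rather than power. A correlation of 0.3 between the tests changes power by about 0.01 or less.

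**5. Type I error.** Section 14.7 puts the inflation at about 0.005. With no true effect and the rule run on the primary outcome, simulated one-sided error is 0.028 against 0.025, an inflation of about 0.003. The stated figure is not contradicted, but it can be checked only once the outcome is named.

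**The case against.** The best defence is that little depends on this interim. The adjustment is optional in the text, and the study is called exploratory. About 60 patients are to be enrolled; with 10% to 15% drop-out that leaves 60 × 0.85 = 51 to 60 × 0.90 = 54, which is already the ceiling of the rule. If the interim cannot be run, the base size of 34 still stands, and the final RBANS test is unchanged. At the design effect, power is 0.808 at 34 and 0.94 at 51 or 52.

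Most of this stands and limits the consequence. It does not remove the contradiction. Section 14.1 says the size remains at 34 when the calculated N is lower, so the rule can end the trial short of 52, and the variable that drives it then matters. Re-estimation is there for the case where the effect is smaller than planned, and that is where the wrong variable costs power.

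Two stronger readings are tempting:

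- A reader might infer that an amendment dropped CPT-III. The contents entry suggests this, but the visible summary of changes records no such removal. The documents support only that the test is not scheduled.
- A reader might infer a loss from 56% to 40% power at a true RBANS change of 0.3. Those are the fixed-sample powers at 51 (0.556) and at 34 (0.397). They compare one branch of the rule with its cap. Rule against rule, with CPT-III d = 0.5, the loss is about 8 points.

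**Conclusion.** The contradiction is real and sits within current text: the only outcome named for the re-estimation is one that the trial does not schedule, describe in the body or list as an endpoint. As written, the pre-specified rule cannot be executed. If CPT-III data were found, a non-endpoint would set the size.

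Under the assumed effects in which CPT-III responds more than RBANS, the loss in power is about 8 to 13 points at a true RBANS change of 0.3 (0.46 to 0.41 against 0.54) and about 8 to 14 points at 0.4 (0.69 to 0.63 against 0.77). If CPT-III shows no change, power is not lost but the cap is nearly always reached. These figures rest on assumed effects, independent tests, a cap of 51 and my reading of how N is calculated.

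The documents do not support a claim that the trial is underpowered for its planned effect, that the 34 is wrong, or that the final RBANS analysis is invalid.

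**What to change.** - In the synopsis (Interim Analysis) and Section 14.7, replace the reference to CPT-III omission with: *the Visit 2 to Visit 3 change in the primary composite score (RBANS Global Composite, or the telephone battery composite if that is the primary battery employed)*. Naming RBANS alone is not enough, because patients tested by telephone may have no RBANS score. State what is done if the first 17 evaluable patients were tested in both modes.
- State that N and K are computed from the mean and SD of that change, with the paired-t method, 80% power and one-sided 0.025.
- Recheck the statement of about 0.005 inflation for that outcome; simulation suggests about 0.003 one-sided.
- Alternatively, delete the interim and fix the target size in advance.
- Separately, and minor: in the synopsis (Sample Size Considerations) and Section 14.1, reconcile r = 1.5, which gives 51, with the stated maximum of 52. One patient changes power at d = 0.5 only from 0.938 to 0.943.

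The cost is wording in two places for the main point and two more for the cap, plus the short recheck. No new data or extra patients are needed. The change should be made before the interim data are examined.

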## **15. LABORATORY VALUE CRITERIA**

Investigator will treat patients based on the local standards.

## **16 PROCEDURES AND INSTRUCTIONS**

### **16.1 Special Safety-Related Procedures**

#### **16.1.1 Instructions for Rapid Notification of Serious Adverse Events**

##### **16.1.1.1 Reporting Responsibility**

**Each SAE must be reported by the Investigator to the IRB for this study according to the guidelines of the IRB of record within 24 hours of learning of its occurrence and IQVIA, the pharmacovigilance provider for intake of SAE forms contracted by Veloxis, the developer of Envarsus XR.**

If the SAE is considered to be related to study drug and confirmed to be unexpected for the investigational product, IQVIA may urgently require further information from the Investigator for health authority reporting.

##### **16.1.1.2 Reporting Procedures**

Serious adverse events must be reported within 24 hours of the occurrence of the event whenever possible, but at least within 24 hours of awareness of the event. The Investigator must complete the AE/SAE CRF with as much information available at the time of completion and transmit an SAE Fax Notification Form to IQVIA (refer to [Section 16.1.1.3](#) for contact numbers).

As follow-up information is received, the Investigator must update the AE/SAE CRF and/or email or fax any written/supporting documentation within 24 hours of receipt of the new information. Investigators should be ready to provide copies of any relevant data from the hospital notes (e.g., electrocardiograms [ECGs], laboratory tests, discharge summary, postmortem results, etc.), if requested. An SAE Notification Form must be completed and faxed to IQVIA when any new information is obtained, or information has been changed in the system on the AE/SAE CRF.

All SAEs should be followed up until resolution or permanent outcome of the event. Refer to the Study-specific Expedited SAE Recording and Reporting Plan for further reporting information.

##### **16.1.1.3 Instructions for Rapid Notification of SAEs and Pregnancies**

Any SAE must be reported on the AE/SAE CRF (refer to [Section 16.1.1.2](#)) IQVIA, the pharmacovigilance provider for intake of SAE forms contracted by Veloxis, the developer of Envarsus XR. Pregnancies and pregnancy follow up should be reported on the Pregnancy Form within the CRF. Pregnancy follow-up should describe the outcome of the pregnancy, including any voluntary or spontaneous termination, details of the birth, the presence or absence of any congenital abnormalities, birth defects, maternal or newborn complications and their relation to this study. Refer to the Pregnancy Completion Guidelines as needed for instructions for completing the Pregnancy Form.

SAE and pregnancy reporting contact numbers (telephone/facsimile) will be generated upon contract execution and including on the reporting form.

## **16.2 Administrative Procedures**

### **16.2.1 Changes to the Protocol**

Any change or addition to this protocol affecting the safety of patients, the scope of the investigation, or the scientific quality of the study requires approval by the IRB. If an immediate change to the protocol is felt to be necessary by the Investigator and is implemented by him for safety reasons, IRB should be notified within 10 working days.

Protocol changes affecting only administrative aspects of the study do not require formal protocol amendments or IRB approval, but the IRB must be kept informed of such administrative changes.

### **16.2.2 Recording of Data and Retention of Documents**

All data will be transcribed into REDCap.

Data on patients collected on CRFs during the study will be documented in an anonymous fashion and the patient will only be identified by the Patient Identification (PID) number and by initials if also required. If, as an exception, it is necessary for safety or regulatory reasons to identify the patient, the Investigator is bound to keep this information confidential.

The Investigator must maintain source documents for each patient in the study, consisting of all demographic and medical information, and must keep a copy of the signed ICF. Patient clinical source documents (usually defined by the project in advance to record key efficacy/safety parameters independent of the CRFs) would include patient hospital/clinic records, physicians' and nurses' notes, appointment book, original laboratory reports, and signed ICFs. All information on CRFs must be traceable to these source documents in the patient's file. Data without a written or electronic record will be defined before study start and will be recorded directly on the CRFs, which will be documented as being the source data.

Essential documents, as listed below, must be retained by the Investigator for as long as needed to comply with national and international regulations. The Investigator agrees to adhere to the document retention procedures by signing the protocol.

Essential documents include:

1. IRB approvals for the study protocol and all amendments;
2. All source documents and laboratory records;
3. CRF copies;
4. Patients' ICFs (with study number and title of study);
5. Form FDA 1572;

### **16.2.3 Auditing Procedures**

The Investigator must understand that source documents for this study must be made available to the IRB and/or to health authority inspectors after appropriate notification. The verification of the CRF data must be by direct inspection of source documents. A regulatory authority may also wish to conduct an inspection (during the study or even after its completion).

### **16.2.4 Publication of Results**

An integrated clinical and statistical report will be generated at the completion of the study. However, it is intended that the results of the study will be included on <http://clinicaltrials.gov> and published and/or presented at scientific meetings.

### **16.2.5 Disclosure and Confidentiality**

By signing this protocol, the Investigator agrees to keep all information provided in strict confidence and to request similar confidentiality from his/her staff and the IRB. Study documents (protocols, CRFs, and other material) will be stored appropriately to ensure their confidentiality.

The Investigator must assure that patients' anonymity will be maintained and that their identities are protected. The Investigator will keep a patient enrollment log relating codes to the names of patients. The Investigator will maintain documents e.g., patients' signed consent forms, in strict confidence.

## **16.3 Ethics and Good Clinical Practice**

This study must be carried out in compliance with the protocol and:

- ICH Guidance on Good Clinical Practice (ICH E6)
- Title 21 of the US FDA Code of Federal Regulations Parts 50 and 56
- World Medical Association. Declaration of Helsinki: Ethical principles for medical research involving human subjects, current version

### **16.3.1 Institutional Review Board**

Before implementing this study, the protocol, the proposed ICF and other information to patients, must be reviewed by a properly constituted IRB. A signed and dated statement that the protocol and ICF have been approved by the IRB must be given to Sponsor before study initiation. The name and occupation of the chairperson and the members of the IRB must be supplied to Sponsor. Any amendments to the protocol, other than administrative ones, must be approved by this committee.

### **16.3.2 Informed Consent**

The Investigator or designee must explain to each patient (or legally authorized representative) the nature of the study, its purpose, the procedures involved, the expected duration, the potential risks and benefits involved and any discomfort it may entail. Each patient must be informed that participation in the study is voluntary and that he/she may withdraw from the study at any time

and that withdrawal of consent will not affect his/her subsequent medical treatment or relationship with the treating physician.

This informed consent should be given by means of a standard written statement, written in nontechnical language. The patient should read and consider the statement before signing and dating it, and should be given a copy of the signed document. If the patient cannot read or sign the documents, oral presentation may be made or signature given by the patient's legally appointed representative, if witnessed by a person not involved in the study, mentioning that the patient could not read or sign the documents. No patient can enter the study before his/her informed consent has been obtained.

The ICF must be submitted by the Investigator for IRB approval. Sponsor will supply a proposed ICF which complies with regulatory requirements and is considered appropriate for the study. Any changes to the proposed ICF suggested by the Investigator must be agreed to by Sponsor before submission to the IRB and a copy of the approved version must be provided to the site monitor after IRB approval.

